#### 9.2.3.1.5 Pregnancy and Lactation

Details of all pregnancies and/or lactation in female subjects and, if indicated, female partners of male subjects will be collected after the start of study treatment and until 30 days (for female subjects) and 90 days (for female partners of male subjects) after the last dose of study drug(s).

If a pregnancy is reported, the investigator is to inform Amgen within 24 hours of learning of the pregnancy and/or lactation and is to follow the procedures outlined in Section 12.5. Amgen Global Patient Safety will follow-up with the investigator regarding additional information that may be requested.

Abnormal pregnancy outcomes (eg, spontaneous abortion, fetal death, stillbirth, congenital anomalies, ectopic pregnancy) are considered serious adverse events.

Further details regarding pregnancy and lactation are provided in Section 12.5.

#### 9.2.3.2 Vital Signs

The following measurements must be performed: systolic/diastolic blood pressure, heart rate, respiratory rate, and temperature. Subject must be in a supine position in a rested and calm state for at least 5 minutes before blood pressure assessments are conducted. If the subject is unable to be in the supine position, the subject should be in most recumbent position as possible. The position selected for a subject at screening should be the same that is used throughout the study and documented on the vital signs CRF. Take at least 2 blood pressure measurements spaced 1 to 2 minutes apart and additional measurements if the first 2 are quite different (Section 12.15). Record the average blood pressure on the vital signs CRF.

The temperature location selected for a subject at screening should be the same that is used throughout the study and documented on the vital signs CRF. Record all measurements on the vital signs CRF.

#### 9.2.3.3 Electrocardiograms (ECGs)

Electrocardiograms will be required for all subjects at screening.

Subject must be in supine position in a rested and calm state for at least 5 minutes before ECG assessment is conducted. If the subject is unable to be in the supine position, the subject should be in most recumbent position as possible. The ECG must include the following measurements: heart rate, QRS, QT, QTc, and PR intervals. The PI or designated site physician) will review all ECGs. The presence of a low voltage ECG coded on the ECG output, will be entered on the appropriate eCRF. Once signed,

Protocol Number: 20170596

**Date**: 20 May 2019 Page 78 of 132

the original ECG tracing will be retained with the subject's source documents. At the request of the sponsor, a copy of the original ECG will be made available to Amgen.

#### 9.2.3.4 Other Safety

#### 9.2.4 Echocardiogram

All subjects will have a baseline transthoracic echocardiogram during screening, including assessments of systolic and diastolic left ventricular function and right ventricular function, valvular insufficiency, right ventricular systolic pressure, intraventricular wall thickness, left and right ventricular wall thickness and left ventricular mass index, mitral annular early diastolic velocity, and left atrium value index.

#### 9.2.5 Clinical Laboratory Assessments

Refer to Section 12.2 for the list of clinical laboratory tests to be performed and to the Schedule of Activities (Table 2-1) for the timing and frequency.

The investigator is responsible for reviewing laboratory test results and recording any clinically relevant changes occurring during the study in the Event CRF. The investigator must determine whether an abnormal value in an individual study subject represents a clinically significant change from the subject's baseline values. In general, abnormal laboratory findings without clinical significance (based on the investigator's judgment) are not to be recorded as adverse events. However, laboratory value changes that require treatment or adjustment in current therapy are considered adverse events. Where applicable, clinical sequelae (not the laboratory abnormality) are to be recorded as the adverse event.

All protocol-required laboratory assessments, as defined in Section 12.2, must be conducted in accordance with the Schedule of Activities (Table 2-1).

#### 9.2.5.1 Pregnancy Testing

A serum or urine pregnancy test must be completed at screening. A highly sensitive (urine or serum) pregnancy test should be completed within 24 hours of initiation of investigational/noninvestigational product for females of childbearing potential (FCBP).

Note: Females who have undergone a bilateral tubal ligation/occlusion should have pregnancy testing per protocol requirements. (If a female subject, or the partner of a male subject, becomes pregnant it must be reported on the Pregnancy Notification Worksheet, see Figure 12-2). Refer to Section 12.5 for contraceptive requirements. Additional pregnancy testing must also be performed during treatment, as per the Schedule of Activities (Table 2-1) and at the safety follow-up visit.

Protocol Number: 20170596

**Date:** 20 May 2019 **Page 79 of 132** 

Additional on-treatment pregnancy testing may be performed at the investigator's discretion or as required per local laws and regulations.

#### 9.2.6 Clinical Outcome Assessments

# 9.2.6.1 European Organization for Research and Treatment of Cancer Quality-of-life Questionnaire Core 30 (EORTC QLQ-C30)

The European Organization for Research and Treatment of Cancer Quality-of-life Questionnaire Core 30 (EORTC QLQ-C30) is a questionnaire developed to assess the quality of life of cancer patients (Bjordal et al, 2000).

EORTC QLQ-C30 includes 30 items grouped into:

- five quality of life categories: physical, social, emotional, cognitive and role performance;
- three scales of symptoms: fatigue, pain, and nausea and vomiting;
- a global scale of quality-of-life and individual items related to the symptoms of the disease and its treatment; dyspnea, insomnia, loss of appetite, constipation, diarrhea and
- an item on economic impact

The responses to the scale items refer to "last week," with the exception of the subject's physical performance scale, where the timeframe involved is the present.

# 9.2.6.2 European Organization for Research and Treatment of Cancer Quality-of-life Questionnaire Multiple Myeloma Module (EORTC QLQ-MY20)

In addition to the QLQ-C30, a number of disease-specific modules have been produced by the EORTC. This modular approach was adopted by EORTC in recognition of the limitations of generic patient-reported outcome instruments to provide an appropriate coverage of disease-specific concerns. Modules specific to tumor site, treatment modality, and quality of life have been developed. These were designed to be administered alongside the core questionnaire (QLQ-C30); like the core questionnaire, the modules were designed for use in cancer clinical trials. The MM module (the QLQ-MY20) was developed by EORTC in 1999 (Bjordal et al, 2000). A summary of the QLQ-C30 and QLQ-MY20 subscales are provided in Section 12.16.

Protocol Number: 20170596

**Date**: 20 May 2019 Page 80 of 132

#### 10. Statistical Considerations

#### 10.1 Sample Size Determination

The study is descriptive in nature. Approximately 75 subjects will be enrolled in the study with approximately 25 subjects in each treatment arm.

The sample size is assessed in terms of the expected levels of precision for estimating the proportion of subjects completing 12 cycles of treatment, relative dose intensity (%), and incidence of adverse events.

With a sample size of 25 subjects for each treatment arm, assuming 50%, 75%, or 90% of subjects will complete 12 cycles of treatment, the expected half-widths of the 95% CI for estimating the proportion of subjects completing 12 cycles of treatment are calculated as below.

	95% Confidence Interval Half-width (%)		
Sample Size	50%	75%	90%
25	20.5	18.1	13.5

In the A.R.R.O.W. trial, the mean (standard deviation) of relative dose intensity of carfilzomib is 92.2 (11.2) in Once-weekly subjects. In this study with a sample size of 25 subjects in each treatment arm, assuming standard deviation ranges from 5% to 15%, the expected half-widths of the 95% CI for estimating the mean relative dose intensity are calculated as below.

	95% Confidence Interval Half-width (%)		
Sample Size	SD = 5	SD = 10	SD = 15
25	2.0	3.9	5.9

For subject incidence of adverse events of 1%, 5%, 10%, 50%, 80%, the expected half-widths of the 95% confidence interval (CI) for estimating the subject incidences of adverse events are calculated as below.

	95% Confidence Interval Half-width (%)				
Sample Size	1%	5%	10%	50%	80%
25	7.8	10.8	13.5	20.5	16.9

Protocol Number: 20170596

**Date:** 20 May 2019 Page 81 of 132

#### 10.2 Analysis Sets, Subgroups, and Covariates

#### 10.2.1 Analysis Sets

Full Analysis Set: The full analysis set will include all enrolled subjects who received at least 1 dose of any study treatment (ie, carfilzomib, dexamethasone. lenalidomide, or pomalidomide).

Safety Analysis Set: The safety population will include all enrolled subjects who received at least 1 dose of any study treatment (ie, carfilzomib, dexamethasone, lenalidomide, or pomalidomide).

The full analysis set will be the same as the safety analysis set for this study.

#### 10.2.2 Covariates

The following covariates will be used to examine primary and secondary endpoints in subgroups as appropriate:

Baseline demographics and characteristics:

- age (as categorical variable: 18 to < 65, 65 to 75, and > 75 years)
- sex (male, female)
- race (white and other categories depending on frequency observed)
- commute distance to treatment center: 0-10, 11-25, > 25 miles

Baseline organ function and comorbid conditions:

- ECOG performance status (0 or 1)
- estimated GFR (< 50 vs ≥ 50 mL/min/1.73 m²)

- hypertension history (include use of anti-hypertensive medications) (yes, no)
- history of ischemic heart disease (myocardial infarction or coronary artery disease), congestive heart failure (NYHA class ≤ 2), stroke, or history of peripheral vascular disease (yes, no)
- family history of coronary artery disease in first degree relatives with onset
   65 years of age for female relative or < 55 years of age for male relative (yes, no)

- smoking history (yes, no)
- history of hyperlipidemia (yes, no)
- history of diabetes (yes, no)
- history or chronic mild hepatic impairment (yes, no; see Section 7.4.1.1.1)

Protocol Number: 20170596

**Date:** 20 May 2019 Page 82 of 132

#### Baseline disease characteristics:

revised international staging system stage (stage 1 vs stage 2 vs stage 3 vs unknown)

- determination of measurable disease at baseline (based on serum or urine M-protein, based on SFLC only)
- $\beta$ 2-microglobulin level (< 2.5,  $\geq$  2.5 and < 5.5,  $\geq$  5.5 mg/L)
- presence of soft tissue plasmacytoma (yes, no)
- progressive disease on lenalidomide during or within 60 days of discontinuation of treatment (yes, no)

#### 10.2.3 Subgroups

The subgroups defined by covariates stated above will be used to examine primary and secondary endpoints as appropriate, including examination of safety in subgroups as appropriate. The subgroup analysis will not be carried out if the number of subjects in a subgroup for any treatment arm is smaller than 20% of the total number of subjects in the treatment arm.

#### 10.2.4 Handling of Missing and Incomplete Data

Subjects may have missing data points for a variety of reasons. The procedures outlined below describing what will be done when data are missing may be refined during the blind review of the data.

Incomplete adverse event start dates, concomitant medications start or stop dates, and death date will be imputed and the detailed rules will be specified in statistical analysis plan (SAP).

#### 10.3 Statistical Analyses

The SAP will be developed and finalized before database lock. Below is a summary of the timing and methods for the planned statistical analyses. To preserve study integrity, the final analysis will be conducted and reported following the end of study, as defined in Section 5.3.1.

#### 10.3.1 Planned Analyses

#### 10.3.1.1 Data Review Team

A Data Review Team (DRT) will review safety data for the KPd treatment arm on an ongoing basis. A DRT is a group, internal to Amgen but external to the relevant carfilzomib product team, that reviews accumulating data from the ongoing clinical trial to ensure no avoidable increased risk for harm to subjects. The DRT includes a clinician, a

Protocol Number: 20170596

**Date:** 20 May 2019 **Page 83 of 132** 

safety physician, and a biostatistician. Membership procedures and meeting timing will be described in detail in the study DRT charter.

#### 10.3.1.2 Final Analysis

The final analysis will occur after all subjects have completed therapy, disease assessments and safety follow-up.

#### 10.3.2 Methods of Analyses

#### 10.3.2.1 General Considerations

In principle, summary statistics including non-missing sample size (n) mean, standard deviation, median, minimum and maximum quartiles, will be provided for continuous variables. Frequency and percentage will be summarized for binary and categorical variables. Proportions and the corresponding 95% confidence intervals will be based on normal approximations unless otherwise specified. The Clopper-Pearson method of exact binomial confidence intervals will be used to calculate the confidence intervals as appropriate.

Details of all the analyses will be provided in the statistical analysis plan, which will be developed and finalized before database lock. To preserve study integrity, the final analysis will be conducted and reported following the end of study, as defined in Section 5.3.1.

#### 10.3.2.2 Efficacy Analyses

Endpoint	Statistical Analysis Methods
Primary	Not applicable
Secondary	Unless otherwise specified, the following analyses will be based on the safety analysis set. The analyses will be carried out for subjects on the Kd, KRd, and KPd regimens, respectively.
	All EORTC QLQ-C30 and EORTC QLQ-MY20 subscale scores up to cycle 12 or disease progression will be summarized descriptively by cycle.
	The rate of PFS at 1 year will be estimated using the Kaplan-Meier method and with CI estimated using the method by Kalbfleisch and Prentice, 1980 with log-log transformation.
	The response rate and 1-year PFS rate will be summarized descriptively by line of prior therapy 1 vs $\geq$ 2.
Exploratory	

Protocol Number: 20170596

**Date:** 20 May 2019 **Page 84 of 132** 

#### 10.3.2.3 Safety Analyses

#### 10.3.2.3.1 Analyses of Primary Safety Endpoint(s)

Endpoint	Statistical Analysis Methods
Primary	Unless otherwise specified, following analyses will be based on the safety analysis set. The analyses will be carried out for subjects on the Kd, KRd, and KPd regimens, respectively.
	The proportion of subjects completing 12 cycles of Kd, KRd, and KPd treatment will be calculated based on the safety analysis set.
	The proportion of actual cumulative dose received to the full intended cumulative dose in cycles 1-12 will be summarized descriptively. The full intended cumulative dose is defined as all therapy specified per Sections 7.1.1.2 and 7.1.2 without consideration for dose modification or skipped doses. Relative dose intensity in cycles 1-12 will be summarized descriptively. Dose modifications including dose reduction, dose withheld, and dose delay in cycles 1-12 will be summarized along with reasons including adverse events and non-adverse events. Treatment-emergent adverse events and serious adverse events in cycles 1-12 will be summarized descriptively following the methods specified in Section 10.3.2.3.
Secondary	Not applicable
Exploratory	Not applicable

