# 4. Objectives, Endpoints and Hypotheses

# 4.1 Objectives and Endpoints

Objectives	Endpoints		
Primary			
Describe adherence and treatment safety across all 12 cycles of carfilzomib based regimens in subjects with relapsed or refractory multiple myeloma with 1-3 prior lines of therapy at study entry.	
 
proportion of subjects completing         12 cycles of treatment
 
proportion of actual cumulative dose         received to the full intended cumulative         dose in cycles 1-12
 
relative dose intensity in cycles 1-12
 
dose modifications and reasons in         cycles 1-12
 
treatment-emergent adverse events and         serious adverse events
 
		
Secondary			
Assess subject health-related quality-oflife (HRQoL) with the Kd, KRd, and KPd regimens.	European Organization for Research and Treatment of Cancer Quality-of-life Questionnaire (EORTC QLQ) Core 30 (C30) and EORTC QLQ Multiple Myeloma Module (MY20) scores through cycle 12 or up to disease progression		
Assess response to the Kd, KRd, and KPd regimens.	
 
response rate (stringent complete response [sCR], complete response [CR], very good partial response [VGPR], partial response [PR], minimal response [MR], stable disease [SD], progressive disease [PD], Not evaluable [NE]).
 
progression-free survival (PFS) at 1 year
 
response rate and PFS by line of prior therapy 1 vs ≥ 2
 
		
Objectives	Endpoints		
Exploratory			

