**Date:** 20 May 2019 **Page 68 of 132** 

local country's regulatory mechanism, based on parameters consistent with Section 12.3.

Reasons for removal from protocol-required investigational product(s) or procedural assessments include any of the following:

- Decision by Sponsor
- Lost to follow-up
- Death
- Ineligibility determined
- Protocol deviation
- Non-compliance
- Adverse event
- Subject request
- Disease progression
- Requirement for alternative therapy
- Pregnancy

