# 8.2.2 Reasons for Removal From Study

Reasons for removal of a subject from the study are:

- Decision by sponsor
- Withdrawal of consent from study
- Death
- Lost to follow-up
- Disease progression (NOTE: safety follow-up visit is required, and will occur 30 (+3) days after the last dose of study drug[s])

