2.1 Objectives and Endpoints

Objectives	Endpoints
Primary	
Describe tolerability and treatment safety of a Kd regimen (Kd 56 mg/m² [Kd56] twice weekly for cycles 1-6 followed by Kd 70 mg/m² [Kd70] once weekly for cycles 7-12) in subjects with relapsed or refractory multiple myeloma with 1-3 prior lines of therapy at study entry.	 Proportion of subjects completing 12 cycles of treatment Dose intensity defined as total actual dose divided by planned dose through cycle 12 or up to disease progression Treatment-emergent adverse events and serious adverse events
Secondary	
Describe treatment adherence by the Kd regimen (Kd56 twice weekly and Kd70 once weekly).	 Dose intensity in cycles 1-6 and cycles 7-12 defined as total actual dose divided by planned dose through cycle 6 or 12 or up to disease progression Dose reductions in cycles 1-6 and cycles 7-12
	 Treatment discontinuation for all reasons in cycles 1-6 and cycles 7-12
Assess subject health-related quality-of-life (HRQoL) with Kd56 twice weekly and Kd70 once weekly.	 European Organization for Research and Treatment of Cancer Quality-of-life Questionnaire (EORTC QLQ) Core 30 (C30) and EORTC QLQ Multiple Myeloma Module (MY20) scores through cycle 12 or up to disease progression EORTC QLQ-C30 and EORTC QLQ-MY20 scores for cycles 1-6 and cycles 7-12 in subjects completing 12 cycles of treatment

Date: 08 June 2018 Page 7 of 27

[MI god cor stri	sponse rate (minimal response R], partial response [PR], very od partial response [VGPR], mplete response [CR], and ingent complete response [sCR]).
12	ndmark response rate (MR, PR, SPR, CR and sCR) after 6 and cycles.
	ogression-free survival (PFS) at rear
	sponse rate and PFS by line of or therapy 1 vs \geq 2
Exploratory	

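### The completion and full-12-cycle dose endpoints count stopping for progression as a shortfall in adherence, and no planned dose measure separates it from other early stopping

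*Protocol*

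**What the plan says.** The primary objective in protocol Section 4.1 is to "Describe adherence and treatment safety across all 12 cycles of carfilzomib based regimens". Its endpoints are completion of 12 cycles, the cumulative-dose proportion, relative dose intensity, dose modifications with reasons, and adverse events.

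Section 10.3.2.3.1 sets two of these as follows:
- Completion: "The proportion of subjects completing 12 cycles of Kd, KRd, and KPd treatment will be calculated based on the safety analysis set".
- Dose proportion denominator: "The full intended cumulative dose is defined as all therapy specified per Sections 7.1.1.2 and 7.1.2 without consideration for dose modification or skipped doses".

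Neither definition treats progression separately. Section 8.1 opens its list with "Reasons for removal from protocol-required investigational product(s) or procedural assessments include any of the following", and disease progression and death are both on that list. Section 8.2.2 also lists progression as a reason for removal from the study.

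The SAP (08 June 2018, written for the protocol of 06 March 2018) still has an endpoint whose denominator ends at progression: "Dose intensity defined as total actual dose divided by planned dose through cycle 12 or up to disease progression". The current protocol's cumulative-dose endpoint has no such limit.

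Other parts of the plan bear on this:
- The protocol synopsis reports discontinuations due to adverse events.
- SAP 9.2 tabulates treatment discontinuation by reason.
- SAP Section 5 defines relative dose intensity per week of exposure.
- SAP 9.6.1 tabulates exposure and dose modifications in the four groups of SAP 9.5.2: stopped for progression by the end of cycle 6, stopped for progression in cycles 7-12, completed 12 cycles, and stopped for any other reason.

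**The concern.** Adherence and tolerability concern whether subjects can and do take the regimen as prescribed. A subject who takes every dose without toxicity and stops because the disease progresses has adhered, yet counts against the regimen on two primary endpoints. A low figure on either can therefore reflect progression, intolerance, inconvenience or a mixture.

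This matters most when the arms are read side by side. Investigators assign treatment, and Section 7.2 recommends KPd for lenalidomide-refractory subjects and KRd for those who are not refractory. Progression risk may plausibly differ by arm, and such a difference could be taken for a difference in adherence.

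**Working it through.** **Reproducing the plan's figure.** Section 10.1 says "With a sample size of 25 subjects for each treatment arm", "assuming 50%, 75%, or 90% of subjects will complete 12 cycles of treatment", and gives 95% half-widths of 20.5, 18.1 and 13.5 points. Clopper-Pearson limits evaluated at x = 25p give 20.46, 18.09 and 13.49, so the figures reproduce.

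**Planned carfilzomib dose (mg/m²), Table 7-1.**
- Kd: cycle 1, 2×20 + 4×56 = 264; cycle 2, 6×56 = 336; cycles 3-12, 10×3×70 = 2100; total 2700.
- KRd and KPd: 2×20 + 4×27 = 148; 6×27 = 162; 10×3×56 = 1680; total 1990.

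**One fully dosed subject who stops after cycle 4.**
- Dose proportion, Kd: (264 + 336 + 2×210)/2700 = 1020/2700 = 37.8%.
- Dose proportion, KRd or KPd: (148 + 162 + 2×168)/1990 = 646/1990 = 32.5%.
- Relative dose intensity, Kd, applying the SAP Section 5 rules to the current schedule and counting planned dose to the last infusion: first dose day 1, last dose day 3×28 + 15 = 99, interval to next planned dose 14 days. Exposure is (98 + 14)/7 = 16 weeks, and planned weeks are 3×4 + 4 = 16. The ratio is (1020/16)/(1020/16) = 100%.

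These values do not depend on why the subject stopped:

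| Measure (Kd, stop after cycle 4) | Stopped for progression | Stopped for any other reason |
|---|---|---|
| Completed 12 cycles | No | No |
| Dose / full 12-cycle dose | 37.8% | 37.8% |
| Relative dose intensity | 100% | 100% |
| Dose / intended dose to cycle 12 or progression (not in the current protocol) | 100% | 37.8% |

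Only the last row separates the two subjects.

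**Arm level.** Assumptions: exponential PFS, treatment stops only for progression or death, and no dose is missed. Duration is 12×28 = 336 days, and 336/30.4 = 11.05 months. Expected completion is 0.5^(11.05/median). The expected dose proportion is Σ d·S(t) / Σ d over the planned doses d at times t. Medians are from protocol Section 3.3.2.

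| Median PFS | Source regimen | Completion | Mean dose proportion |
|---|---|---|---|
| 11.2 months | Kd once weekly (A.R.R.O.W.) | 50.5% | 74.8% (Kd schedule) |
| 18.7 months | Kd twice weekly (ENDEAVOR) | 66.4% | 83.7% (Kd schedule) |
| 26.3 months | KRd twice weekly (ASPIRE) | 74.7% | 87.1% (KRd schedule) |

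If dosing runs to the end of the cycle in which progression occurs, simulation of 200,000 subjects gives mean dose proportions of 75.9%, 84.4% and 87.7%. The documents give no KPd median, so that arm cannot be computed.

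**The same completion rate from different causes.**
- A: median PFS 11.2 months, no other stopping. Completed 50.5%, progression or death 49.5%, other 0%.
- B: median PFS 26.3 months, hazard ln2/26.3 = 0.0264 per month, plus a hazard of 0.0355 for other reasons. The total is 0.0619 = ln2/11.2, so completion is again 50.5%. Progression or death takes (0.0264/0.0619)×49.5% = 21.1%, and other reasons take 28.4%.

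Crude completion is identical; the split by cause is not.

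**The case against.** A reader might infer that a perfectly tolerated regimen could not be told apart from a poorly tolerated one, so that the trial cannot answer its adherence question. The documents do not support that. The SAP tabulates all reasons for stopping, the protocol reports adverse-event discontinuations, and relative dose intensity, itself a primary endpoint, is not lowered by stopping at progression. The SAP's four-group split already sets progressors apart in the exposure and dose-modification tables. If every subject's treatment outcome is known at the final analysis, the proportion stopping for other reasons follows from the reasons table.

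Three limits remain. The SAP predates the KRd and KPd arms. Its groups divide at the end of cycle 6, whereas the schedule now changes at cycle 3, and deaths fall under other reasons. Relative dose intensity ignores all early stopping while the other two endpoints penalise all of it, so none isolates non-progression stopping.

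A reader might also infer that 75% or 90% completion is a target that progression alone would defeat. Section 10.1 uses those values only as a grid for interval width. The study is descriptive, with no threshold and no planned comparison between arms.

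The full-dose denominator may be deliberate: the objective spans all 12 cycles, and the rationale for Amendment 2 mentions clarifying the dose-intensity language. That is a reason to keep the measure, and the proposal does.

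The medians are also imperfect. The 11.2-month figure comes from patients with 2 or 3 prior lines, while this trial admits 1 to 3. The 18.7- and 26.3-month figures come from twice-weekly schedules. In CHAMPION-1, subjects not refractory to bortezomib had medians of 19.4 and 21.0 months, which would give 67.4% and 69.4% completion. PFS also counts deaths, some of which may be toxic.

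**Conclusion.** The point holds for the two endpoints read alone. Under the stated assumptions, progression or death alone would hold completion to about 50-66% in Kd and about 75% in KRd, and the mean carfilzomib dose proportion to about 75-88%. The dose proportion is affected less than completion, and calling it mainly an efficacy measure would go too far. The figures rest on exponential PFS, on medians borrowed from other populations and schedules, and on the current dosing schedule. They do not cover KPd or the Kd subjects kept on six twice-weekly cycles.

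The remaining gap is specific: no planned dose measure penalises stopping for other reasons while leaving progression unpenalised, and the existing split has not been carried into a three-arm plan. Closing it is an inexpensive improvement; the design does not need to change.

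**What to change.** In protocol Section 10.3.2.3.1 and an updated SAP 9.6.1, keep both crude endpoints and add for each arm:

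1. The proportions of treated subjects who completed 12 cycles, stopped for progression, died (with cause shown), or stopped for any other reason. Give a 95% CI for the last. Clopper-Pearson suits, as the SAP already uses it for completion; for 0 of 25 it runs from 0 to 1 − 0.025^(1/25) = 13.7%. If any subject is censored, use cumulative incidence with progression and death as competing events.
2. The cumulative-dose proportion with intended dose counted to cycle 12 or to progression, whichever comes first, shown beside the full 12-cycle version.

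Base adherence statements on these two together with relative dose intensity.

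The cost is wording and two summaries per arm. Stop reasons and progression assessments are already part of the plan, and the SAP needs updating for the three-arm protocol anyway. The downside is that both additions depend on the recorded stop reason and progression date, which the investigator determines in an open-label study.
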